
Planned Sample Size
	
Based on published data, the average pain felt by ladies post uterine artery embolization is 7/10 with a standard deviation of approximately 2.5. The published study of SHGNB for UAE demonstrated a decrease in pain from 7 to 2-5 depending on the analgesics regimen used. We

	
opted for the conservative drop in pain scale from 7 to 5 with a standard deviation of 2.5. This gives an effect size of 0.8. With type I error (alpha) set at 0.05 and type II error (beta) set at 0.2 (power of 80%), the sample size calculations yields a needed sample size of 42. We expect up to a 20% drop out rate due to loss to follow-up, giving a total sample size needed of 50, leaving 25 patients per group.
 
Since the pain drop can be more significant than the conservative value we have opted to use, we suggest an interim analysis that would be expected to give us statistical significance if the pain scale was improved by 50% from 7-3.5 (4 being the number usually used by the recovery room to decide to release patients). Based on similar calculations, to show this level of improvement (taking in account a similar drop out rate), one would need a total of 20 patients and therefore we plan on doing an interim analysis at 20 patients having completed the study to see if there is any need to continue the study or not.

Inclusion Criteria	
 1. Women with symptomatic fibroids or adenomyosis that have requested and been approved for uterine artery embolization 2. Age of patients ranging between 35 and 60 years old 3. Ability to comply with the requirements of the study procedures

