Safety	
 ▪ Possible adverse events the SHGNB would include: 
 ▪ Infection ▪ Bowel injury ▪ Vascular injury/Bleeding ▪ Pain or nerve injury ▪ Allergic reaction to the anesthetic agent ▪ Intravascular injection of the anesthetic agent which can lead to cardiac arrhythmias or seizures ▪ Hospitalization or emergent surgery 
The rate of significant complications is estimated to be less than 0.5%.
 
In the sham group, the only significant risks would be infection and allergic reaction to the anesthetic agent.
 
 ▪ Expected possible adverse events of the uterine artery embolization, independent of SHGNB or not 
 ▪ Pain ▪ Vascular injury/Bleeding ▪ Embolization material migrating to non-targeted organs ▪ Premature ovarian failure ▪ Uterine infection leading to possible hysterectomy ▪ Pulmonary Embolus ▪ Leaving a uterine sarcoma unresected 
Other than pain, which is almost universal and premature ovarian failure that can occur in 2-10% of patients, the other risks are in the order of 1-2% or less. Other than pain, it is expected that these complications will be independent of whether a SHGNB is

	
performed or not.
 
Subjects with procedure related adverse events will be followed up until the resolution of the event.
 
A medical monitor will analyze all serious adverse events (“SAE”) in order to confirm that they are unrelated to the research protocol.

Statistical Methods	
Descriptive statistics will be provided for the efficacy outcome results and will be presented in terms of percentage, frequency, means and 95% confidence interval. Differences between both groups will be compared using Chi-square test for categorical variables and, after verifying a normal distribution to the data, a Student’s t- test for the continuous variables. Regression analysis will be performed to compare time dependent events.

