accordingly. We expect that the data analysis will consist of regression analysis of the temporal pain level distribution between the group with and without the SHGNB. Continuous variable data, with normal distributions, subgroup analysis of the secondary objectives will be compared using a Student's t- test.

▪ **Sample size calculation**

Sample size calculations are based on published data showing the average pain felt by ladies post uterine artery embolization being of 7/10 with a standard deviation of approximately 2.5. The published study of SHGNB for UAE demonstrated a decrease in pain from 7 to 5-2 depending on the analgesics regimen used [6]. We opted for the conservative drop in pain scale from 7 to 5 with a standard deviation of 2.5. This gives an effect size of 0.8. With type I error (alpha) set at 0.05 and type II error (beta) set at 0.2 (power of 80%), the sample size calculations yields a needed sample size of 42. We expect up to a 20% drop out rate due to loss to follow-up, giving a total sample size needed of 50, leaving 25 patients per group. [8]

If the analysis of the data after recruiting 50 patients is highly suggestive of an effect but without statistical significance, and if the calculations suggest we could get statistical significance by doubling the number of participants, and there have been no significant adverse events from the nerve block, we would increase the number of patients to 100. If adverse events have occurred, the number would not be increased unless approval by the ethics committee.

▪ **Interim analysis**

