The previous sample size has been calculated with a conservative number, but the decrease in pain can be as large as from 7 down to 2 based on previous studies. Therefore the above estimation may necessitate more patients than are needed to prove clinical worthiness of the procedure. Clinically, our group feels that we would proceed with the block if we could get at least a 50% decrease in pain from 7 down to 3.5 (a scale of 4 being the common number used for discharge of patients from the recovery room). If a similar sample size calculations is performed for such a drop, a total sample size of 16 would be needed. With a similar drop out rate it is our feeling that an interim analysis should be performed at a patient study completion number of 20, so as to avoid recruiting an excessive number of patients to prove the value of the procedure. Therefore we would perform an interim analysis at 20 patients having completed the study. If the data is statistically significant the study would be terminated early.

6. Study Population

The target population who will be included to participate in this study is all women referred to us for a UAE procedure.

6.1. Inclusion criteria:

1. Women with symptomatic fibroids or adenomyosis that have requested and been approved for uterine artery embolization
2. Women age 35-60 y.o.
3. Ability to comply with the requirements of the study procedures

6.2. Exclusion criteria:

1. Patients in whom the vascular anatomy prevents access to the superior hypogastric nerve plexus safely
2. Patients who have known allergy to the anesthetic agent
3. Patients with signs of skin infection at the entry site of the needle used to place the nerve block
4. Patients with signs of infection such as fever
5. Patients with history of inflammatory bowel disease or with signs of colitis
6. Patients with uncorrectable abnormal coagulation status (INR >1.5 and plt < 50000 without use of anticoagulation agents)
7. Patients with preexisting conditions, which, in the opinion of the investigator, interfere with the conduct of the study.
8. Patients who are uncooperative, cannot follow instructions, or who are unlikely to comply with follow-up appointments or fill-out the post-procedural pain questionnaires.
9. Patients with a mental state that may preclude completion of the study procedure or is unable to provide informed consent

6.3. Randomization:

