Subject data collection at the time of enrollment will include demographics, relevant medical history and vital signs. Subjects will be followed-up as outlined in Table 1 to assess adverse events related to the procedures and clinical success of the procedure. Individual data collection will be considered complete at the time of the follow-up consultation 4-6 months after the UAE procedure.

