Data integrity will be maintained throughout the study. Logic rules within the database will be used to maximize integrity, and random data validation checks will be performed routinely. The research investigator will review studies and patients' data on a monthly basis to ensure that patient follow-up is proceeding as expected. All cases where the research investigator finds a discrepancy in imaging interpretation or outcome assessment will be reviewed by the Adjudication Committee, consisting of the principal investigators. An independent radiologist from the MUHC will be asked to determine the outcome of a dispute amongst the Adjudication Committee.

8. Data Analysis:

Data will be collected and tabulated using the commercially available JMP10/SAS statistical analysis software (SAS Institute Inc., Cary, NC, USA). Descriptive statistics will be provided for the efficacy outcome results and will be presented in terms of percentage, frequency, means and 95% confidence interval of the means. Differences between both groups will be compared using the Chi-square test for categorical variables and Student's t- test for the continuous variables. ANOVA test and multivariate logistic-regression analysis will be used to compare interplay of more than two variables. Two-tailed p-values of less than 0.05 will be set for statistical significance.

9. Ethical considerations:

Research Ethics approval from the MUHC Research Ethics Board office will be obtained prior to the commencement of the study or related research procedures. All patients will be informed about the data that will be gathered for the study. All patients will have the ability to refuse participating in the study as soon as they are able to evaluate it and give their approval or not. Patients will always be given options to ask questions at any time and questions will be answered in a non-intimidating way so as to try to avoid influencing the patient's decision. At any time, the patient can decide to remove himself from the study. If this is the case, he will receive the standard of care.

No unique patient identifying data will appear on the sheets that will be coded only by study identification number. A key linking the patient name and study identification number will be maintained in a separate database. All datasheets will be kept in a locked, dedicated research office. All computer records will be maintained in a

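### The plan does not say what is reported after a stop at 20 completers, and the ordinary estimate from those 20 would overstate a true 2-point benefit by about half

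*Combined protocol and SAP*

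**What the plan says.** The synopsis (Planned Sample Size) announces one look: "we plan on doing an interim analysis at 20 patients having completed the study to see if there is any need to continue". Section 5 (Interim analysis) gives the rule: "If the data is statistically significant the study would be terminated early". It states no separate significance level for the look. The only level in the document is in Section 8: "Two-tailed p-values of less than 0.05 will be set for statistical significance".

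On reporting, the synopsis (Statistical Methods) and Section 8 both say "Descriptive statistics will be provided for the efficacy outcome results", as means with 95% confidence intervals, and compare the groups by Student's t-test. Neither place distinguishes a trial that stops at the look from one that runs to the end.

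Section 7.1 defines when a woman counts as complete: "Individual data collection will be considered complete at the time of the follow-up consultation 4-6 months after the UAE procedure". The home pain sheets run only to day 10 (Section 7.5). The document plans no pause in recruitment before the look.

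**The concern.** The trial stops at the look only if the observed difference is large enough to be significant in 20 women. The ordinary mean difference in a stopped trial is therefore a selected value and lies above the truth on average. This is a problem of estimation, separate from the type I error of testing twice.

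The size of the effect matters here as well as its sign. The study rationale expects a final conclusion on a semi-invasive procedure, and Section 5 says the group would use the block if pain fell by at least half, from 7 to 3.5. A stopped trial with a true benefit of 2 points could appear to meet that bar. Women treated while the first 20 await their 4-6 month visit could supply data not selected by the stopping rule, but the plan does not say whether they count.

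**Working it through.** **Inputs.** Section 5 (Sample size calculation): "We opted for the conservative drop in pain scale from 7 to 5 with a standard deviation of 2.5", and "This gives an effect size of 0.8", since 2/2.5 = 0.8. The look was sized for a drop of 3.5 points (3.5/2.5 = 1.4 SD). The threshold is two-sided p<0.05 (Section 8). Assumptions: the 20 completers split 10 and 10, and each contributes one normally distributed pain score.

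**The plan's own figures.** The totals of 42 and 16 before dropout reproduce with a t-test at one-sided 0.05 and 80% power: 20.03 per arm, so 21 (42 in all), and 7.10 per arm, so 8 (16 in all). At two-sided 0.05 the totals are 52 and 20. Because Section 8 is two-tailed, the two-sided level is used below and the one-sided level is a sensitivity case.

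**What a stop requires.** At an observed SD of 2.5, the smallest significant difference is t(0.975; 18) × SD × √(2/10) = 2.101 × 2.5 × 0.447 = 2.35 points. This already exceeds a true benefit of 2.

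**Mean estimate given a stop** (1,000,000 simulated trials for the true effects of 2 and 3.5):

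| True benefit | Stops at look | Mean reported | Overstatement |
|---|---|---|---|
| 2 | about 40% | 3.03 | +51% |
| 3 | 72% | 3.50 | +17% |
| 3.5 | 84% | 3.80 | +9% |
| 5 | 99% | 5.03 | +1% |

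Hand check at 2 points with the SD treated as known: SE = 2.5 × √0.2 = 1.118; cut-off 1.96 × 1.118 = 2.191; z = (2.191 − 2)/1.118 = 0.171. The mean given a stop is 2 + 1.118 × φ(0.171)/[1 − Φ(0.171)] = 2 + 1.118 × 0.393/0.432 = 3.02.

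Sensitivity at a true 2 points: one-sided 0.05, +40%; an 8/12 split, +54%; scores clipped to 0-10, +52%; SD 2.0, +30%; SD 3.0, +74%.

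**Against the group's own bar.** With a true benefit of 2, the chance of observing 3.5 or more is 1 − Φ(1.5/1.118) = 0.090. Nearly all such results are significant, so about 0.090/0.395 = 23% of stopped trials would appear to meet the bar.

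**Stricter interim level** (true benefit 2; continuing trials end at 25 per arm; 200,000 trials per level):

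| Interim p | Stops | Mean if stopped | Mean if continued | Mean over all runs | 95% CI coverage if stopped |
|---|---|---|---|---|---|
| 0.05 | 39.6% | 3.03 (+51%) | 1.73 | 2.24 | 94% |
| 0.0294 | 30.5% | 3.20 (+60%) | 1.79 | 2.22 | 92% |
| 0.0054 | 11.9% | 3.67 (+84%) | 1.91 | 2.12 | 79% |

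The all-runs mean is a weighted average, for example 0.396 × 3.03 + 0.604 × 1.73 = 2.24.

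**Including women already randomised.** With m further women, balanced between arms and unselected, the pooled mean is close to (20 × 3.03 + m × 2)/(20 + m). For m = 8: 76.6/28 = 2.74. For m = 12: 84.6/32 = 2.64. For m = 20: 100.6/40 = 2.52. Simulation gives the same values. These values of m are assumptions, because the document gives no accrual rate.

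**The case against.** Several points on the other side stand.

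- **Use of the 20-patient estimate is inferred.** A reader might take the plan to say that a stopped trial reports those 20 women and no others. No section says so, and including women already treated is an equally open reading.
- **About half is the top of the plan's own range.** Section 5 cites drops of 2 to 5 points. Across that range the trial is most likely to stop where the overstatement is smallest. At the 3.5 points used to size the look, it is 9%.
- **The interval largely holds under the plan's own rule.** A reader might infer that the ordinary 95% interval fails after a stop. At a true 2 points and p<0.05 it covers in about 94% of stopped trials. Marked under-coverage needs a smaller true effect than the plan considers or a stricter level than it contains.
- **A stricter level is not harmful overall.** A reader might infer that correcting the interim level does damage. The larger overstatement applies only among trials that stop. There are fewer of these, and the all-runs mean moves towards the truth (2.24 to 2.12). Two uncorrected looks, at 20 and 50, give a type I error of about 8.8%, so the boundary is needed.
- **Bias-adjusted estimators are not a clear remedy.** Conditioning on having stopped gave a root mean squared error of 1.25 against 1.19 for the ordinary mean. An approximate check of Whitehead's estimator, which targets the bias over all runs, moved 3.04 only to 2.83.
- **The model is simple.** Pain is scored repeatedly and analgesic use is also primary, but the plan does not name the variable tested at the look. The possible extension to 100 women is not modelled.

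These points limit the size of the concern. They do not supply the missing rule on what is reported after a stop.

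**Conclusion.** The point holds in a limited form. The plan stops on ordinary significance at 20 completers, provides only unadjusted means and intervals, and is silent on reporting after a stop. If the 20-patient estimate became the result, it would overstate the benefit on average by 51% at a true 2 points, 17% at 3 and 9% at 3.5. These figures rest on 10 per arm, SD 2.5, one pain score per woman and two-sided p<0.05. The fault lies mainly in the point estimate after a stop: over all runs the bias is about +0.2 points, and coverage at 2 points is near nominal. An interim boundary is required for the error rate but does not by itself repair this estimate. The documents do not support the stronger readings that the trial is committed to reporting only 20 women, or that tightening the level is a mistake. The change should be made before the look, because a choice of estimate made after seeing the data would not be credible.

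**What to change.** Add the following to the synopsis (Planned Sample Size), Section 5 (Interim analysis) and Section 8:

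1. If the trial stops at the look, the headline effect and its 95% interval come from all women randomised by the date of the decision, once their scheduled pain and analgesic data are complete.
2. The 20-patient estimate is labelled as interim and reported with a statement that stopping on significance inflates it.
3. Any stopping-adjusted estimate is a sensitivity analysis only, with its method fixed before the look.

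This does not replace an interim significance boundary, which is needed separately.

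**Cost.** A few sentences and one further run of the planned analysis. No extra women are recruited, since those added are already randomised. The headline figure will probably be less favourable. There is also a wait for outstanding diaries, which may last until the 4-6 month visit because Sections 7.4 and 7.5 and Appendix IV let women return paper sheets then. The gain depends on how many further women have been randomised: with 8 to 20 of them, the average at a true 2 points falls from 3.0 to about 2.7 to 2.5, so some overstatement remains.

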1.0 Background

1.1. Uterine Fibroids

Uterine fibroids are a monoclonal tumor of smooth muscle origin. Their cause is unknown but is known to be hormone responsive, being diagnosed only after menarche and decreasing after menopause [1].

Uterine fibroids are the most common pelvic tumors in women being present in >80% of black women and approaching 70% in white women in their late 40s. Of these, 50% of black women and 35% of white women have clinical symptoms caused by the fibroids [1]. In 2008-2009, the estimated rate of hysterectomies in Canada was 338/100000 women > 20 years old, with an estimated \$192 million dollars in associated hospitalization costs (Canadian Institute for Health Information). Of these, abnormal menstrual bleeding and fibroids remain the most common reason for hysterectomies. The most common clinical symptoms associated with fibroids are increased bleeding during menstruation, increased pelvic pain especially during menstruation or sexual intercourse, and pressure effects on surrounding structures causing increased urinary frequency and constipation. These symptoms can be very debilitating.

Fibroids are almost exclusively benign in nature. However they can be difficult to differentiate from malignant sarcomas. Fortunately such sarcomas are rare, being estimated at 0.2% or less in surgical series [2].

1.2. Uterine artery embolization

In view of the low risk of malignancy and the complications and cost associated with hysterectomies, there has been a push towards less invasive approaches to treat fibroids. In the mid-late 1990s, the first few publications were released presenting intra-arterial embolization as a method to deplete the fibroids of their blood supply and induce their necrosis, to treat symptomatic fibroids [3]. The procedure consists of obtaining intra-arterial access as is performed routinely for angiographic studies. A catheter is advanced into the uterine arteries on both sides and small plastic based particles are injected. The particles are carried by the blood to the fibroids where they act as plugs as the vessels divide and reduce their size, becoming smaller than the particles themselves. By doing this, the arterial blood supply to the fibroids can be blocked. The result is ischemic fibroids that then undergo necrosis.

The procedure used for the UFE is the same as is presently used at the MUHC. It is performed in the angio unit with the help of fluoroscopy. Access is obtained in the right common femoral artery followed by placement of a vascular sheath. Through the sheath, a 4Fr DAV or 5Fr Cobra catheter and guidewire are used to cannulate the uterine arteries. If there is evidence of spasm, a microcatheter is used. Once the catheter is advanced into the horizontal portion of the uterine artery, an angiographic image is obtained to confirm absence of non-uterine vessels distal to the catheter, such as vessels feeding the vagina that could be damaged by the embolization. After confirmation that no non-targeted vessels are seen, PVA 500-700 particles, suspended into 15-20 ml of a mixture of 50:50 contrast:saline, are injected slowly into the uterine artery until there is loss of visualization of the fibroid blushes and stagnation of contrast in the uterine artery so that the contrast remains present in the artery for a total of at least 5 heart beats. After the left

artery has been treated, the right artery is treated in the same fashion. After the treatment, the catheters and sheaths are removed, pressure is applied to the groin for hemostasis, and the patient is transferred to the recovery room.

The UFE procedure has been found to be safe and effective with fewer complications than total hysterectomy. Approximately 80-90% of women get clinical improvement after uterine artery embolization and 97% would recommend the procedure to others [4]. The most common complication which is almost universal, is that of pain post embolization.

1.3. Pain from Uterine artery embolization

When UAE was first started, the need for pain control was evident. Although it was initially done with general anesthesia in the USA, it was quickly found that this was not necessary. However almost everyone admitted the patient overnight with morphine based patient controlled analgesia (PCA). The use of PCA pumps allowed careful assessment of the pain course after UAE. The information gathered shows a maximal pain threshold reached at approximately 2 hours post-procedure, which lasts 3-4 hours and then a gradual decrease to a lower plateau over another 4-6 hours. This period of decrease to a lower pain plateau is the time during which attempts at discharging the patients from the hospital with oral pain medication is attempted [5]. Most women declare no longer having embolization related pain after 7-10 days.

Because of limited availability to hospital admission after radiological procedures at the MUHC, and the need to offer this less invasive treatment of uterine fibroids to women, the interventional radiologists at the MUHC have offered the procedure with an aggressive IV/Oral sedation protocol while in recovery and discharge orders 4-5 hours after the end of the procedure. The patients are sent home with oral pain medication. However despite this aggressive protocol, approximately 5-10% of patients need admission, not without difficulties at times due to the chronic shortage of beds. This is primarily because this time point of attempted home discharge from the recovery room is still in the phase where the lower more tolerable pain plateau, usually reached only approximately 8 hours after the procedure, has not been reached yet. Even in those that are successfully sent home, they report significant discomfort upon discharge from the hospital and there are some that return to the emergency department for pain management.

In addition there is very little published data regarding pain management once the patients have been discharged home. In an attempt to evaluate this, we have established an online survey that patients can voluntarily fill out to allow us to evaluate this in the future and to flag patients having significant pain, so as to offer a better service to these patients. The patients sign in using an anonymous number assigned to them on the day of the UAE. We would be using this survey in this study and as secondary goal, we will be assessing ease of use of this survey by the patients. Alternatively, the patients can fill a paper based survey if they prefer.

